5 TARGET POPULATION

5.1 INCLUSION CRITERIA

1. Male, age ≥ 18 years old.
2. Karnofsky Performance Status (KPS) of ≥ 70 .
3. Histologic evidence of adenocarcinoma of the prostate who are deemed candidates for curative radical prostatectomy.
4. Planned robotic or laparoscopic prostatectomy technique.
5. Low risk for conversion to open prostatectomy, in the opinion of the treating surgeon.
6. Intermediate-high or high risk, clinically localized disease by the following criteria:
 - Prostate cancer in at least 2 cores with a Gleason score ≥ 7 (4+3 or 3+4) in at least 1 of those cores.
 - No definite evidence of metastasis, in the opinion of the investigator.
7. Adequate organ function as defined by the following criteria within 14 days prior to first dose of study treatment:
 - Aspartate transaminase (AST) and alanine transaminase (ALT) ≤ 3 x local laboratory upper limit of normal (ULN)
 - Total serum bilirubin ≤ 1.5 x ULN, (for subjects with Gilbert's disease ≤ 3 x ULN)
 - Absolute neutrophil count (ANC) ≥ 1500 /L without granulocyte colony-stimulating factor support.
 - White blood cell count ≥ 2500 /mm³
 - Serum albumin ≥ 2.8 g/dl
 - Platelets $\geq 100,000$ /mm³
 - Hemoglobin ≥ 9.0 g/dL
 - Serum calcium ≤ 12.0 mg/dL
 - Serum creatinine ≤ 2.0 x ULN or calculated creatinine clearance ≥ 30 mL/min.
 - Urine protein/creatinine ratio (UPCR) ≤ 1 mg/mg (≤ 113.2 mg/mmol).
8. Written Authorization for Use and Release of Health and Research Study Information (HIPAA authorization per institutional requirements)
9. Evidence of a personally signed and dated informed consent document indicating that the subject has been informed of all pertinent aspects of the trial.
10. Willing/able to adhere to the prohibitions and restrictions specified in this protocol.
11. Agrees to use a condom (even men with vasectomies) and another effective method of birth control if subject is having sex with a woman who is pregnant or a woman of childbearing potential while on study drug and for 4 months following the last dose of study drug.

5.2 EXCLUSION CRITERIA

Subjects cannot have the following:

1. Prior treatment for prostate cancer.
2. Major surgery or radiation therapy within 4 weeks of Day 1 on study.
3. Planned radiation therapy until at least 4 weeks after prostatectomy.

4. NCI CTCAE v5.0 grade 3 hemorrhage within 4 weeks of Day 1 on study.
5. Prothrombin time (PT)/INR or partial thromboplastin time (PTT) test $\geq 1.3 \times$ the laboratory ULN within 14 days before Day 1 on study (Arm A subjects only) or within 14 days of the completion of screening (Arm B subjects only)
6. Concomitant anticoagulation with oral anticoagulants (e.g., warfarin, direct thrombin and Factor Xa inhibitors) or platelet inhibitors (e.g., clopidogrel). However, low-dose aspirin for cardio protection is allowed (per local applicable guidelines).
7. History of or known metastatic prostate cancer.
8. QT_{cf} interval > 500 msec on baseline EKG.
9. The subject has uncontrolled, significant intercurrent or recent illness including, but not limited to, the following conditions:
 - a. Cardiovascular disorders:
 - i. Symptomatic congestive heart failure (CHF) New York Heart Association Class 3 or 4, unstable angina pectoris, ongoing cardiac dysrhythmias of NCI CTCAE grade ≥ 2 . coronary/peripheral artery bypass graft (CABG), within 6 months prior to screening.
 - ii. Stroke (including transient ischemic attack [TIA]), cerebrovascular accident (CVA), myocardial infarction (MI), or other ischemic event, or thromboembolic event (e.g., deep venous thrombosis, pulmonary embolism (PE)) within 6 months prior to screening.
 - b. Gastrointestinal (GI) disorders including those associated with a high risk of perforation or fistula formation:
 - i. Evidence of tumor invading the GI tract, active peptic ulcer disease, inflammatory bowel disease (e.g., Crohn's disease), diverticulitis, cholecystitis, symptomatic cholangitis or appendicitis, acute pancreatitis, acute obstruction of the pancreatic duct or common bile duct, or gastric outlet obstruction.
 - ii. Abdominal fistula, GI perforation, bowel obstruction, or intra-abdominal abscess within 6 months before first dose.
Note: Complete healing of an intra-abdominal abscess must be confirmed before first dose.
 - c. Clinically significant hematuria, hematemesis, or hemoptysis of > 0.5 teaspoon (2.5 ml) of red blood, or other history of significant bleeding (e.g., pulmonary hemorrhage) within 12 weeks before first dose.
 - d. Serious non-healing wound/ulcer/bone fracture.
 - e. Other clinically significant disorders that would preclude safe study participation.
10. Hypertension that cannot be controlled by medications ($>140/90$ mm Hg despite optimal medical therapy).
11. Pre-existing thyroid abnormality with thyroid function that cannot be maintained in the normal range with medication.
12. Concurrent treatment on another clinical trial. Supportive care trials or non-treatment trials, e.g. QOL, are allowed.
13. Other severe acute or chronic medical or psychiatric condition or laboratory abnormality that may increase the risk associated with study participation or study drug administration, or may

interfere with the interpretation of study results, and in the judgment of the investigator would make the subject inappropriate for entry into this study.

14. Inability to swallow tablets.
15. Diagnosis of another malignancy within 2 years before first dose of study treatment, except for superficial skin cancers, or localized, low grade tumors deemed cured and not treated with systemic therapy.

6 STUDY ASSESSMENTS

The first 6 subjects assigned to cabozantinib treatment will constitute the *Safety Lead-In cohort*, which will be only accrued at Duke. Of these subjects, the first 3 subjects will be enrolled sequentially (after each prior subject completes the day 57-85 safety visit). This will constitute the *Safety Lead-In Cohort Part A*. After 3 cabozantinib treatment patients are accrued sequentially, the remaining 3 cabozantinib treatment subjects will be accrued non-sequentially, constituting the *Safety Lead-In Cohort Part B*.

If there are ≥ 2 dose-limiting toxicities (DLTs) in the first 6 subjects receiving cabozantinib, the trial will be stopped for safety purposes (*first stopping rule*). DLTs are defined as CTCAE v5 grade ≥ 2 wound dehiscence or wound complication, any grade fistula, grade ≥ 2 hemorrhage of any type, grade ≥ 3 infections [except urinary tract infections (UTIs) which are expected in this population], any AE that leads to permanent discontinuation of cabozantinib, or other grade ≥ 3 cabozantinib-related perioperative complications. The DLT period is defined as day 1 of drug through day 57 of the protocol (inclusive). The seventh subject receiving cabozantinib may not be enrolled until the sixth subject completes the day 57-85 safety visit *and* the Duke principal investigator agrees that the stopping rule should not be put into effect. From the seventh subject on, subjects may be accrued at ex-Duke site(s). A second stopping rule will be triggered if there are ≥ 3 DLTs in the first 12 subjects treated with cabozantinib. In the event that a stopping rule is triggered, thorough review of the cabozantinib-treated patients' files will be performed and the Duke principal investigator will consider whether the trial can be redesigned or should be permanently discontinued.

Subjects assigned or randomized to receive cabozantinib will receive 28 days of study drug. The washout time between the last dose of cabozantinib and surgery will be 14 days (window: +3 days). Reasons for early discontinuation of cabozantinib may include evidence of disease progression, unacceptable toxicity associated with cabozantinib, withdrawal of consent, or other reasons that may impact on the subject's ability to undergo prostatectomy.

Subjects will be monitored closely for toxicity, and the cabozantinib dose may be adjusted from the 40 mg dose level to 20 mg daily according to individual patient tolerance. Patients will be assessed for adverse events every 2 weeks for the 4 weeks during cabozantinib treatment and at approximately 3 weeks and 4-6 weeks following the final day of cabozantinib administration.

Plasma and serum correlative studies will generally be drawn at baseline, day 29, and day 57-85 in the cabozantinib arm and baseline in the immediate prostatectomy arm. Tissue will be collected for analysis at prostatectomy on both arms.

See **Figures 2** and **3** below for full details of study assessments.

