Exploratory Objectives:	
 1. To estimate the pathologic complete response rate (pCR) and \leqpathologic T2 (\leqpT2) rate in each arm. 2. To evaluate relapse-free survival in each arm. 3. To compare apoptosis (TUNEL), proliferation (Ki-67), and microvessel density (CD31) indices in prostatectomy specimens from patients who undergo immediate prostatectomy versus those treated with cabozantinib prior to prostatectomy. 4. To measure expression levels of c-MET, VEGF, and HGF, as well as activation status of c-MET in prostate tissue. 5. To describe changes in plasticity signaling markers associated with prostate tumors, including vimentin, AR, SNAIL, AXL, and N-cadherin with cabozantinib exposure. 6. To evaluate PTEN and p53 genomic and protein expression status in tumor tissue 7. To demonstrate that cabozantinib is safe and tolerable in patients undergoing radical prostatectomy. 8. To demonstrate that surgery is safe and feasible in patients undergoing treatment with cabozantinib. 9. To collect plasma angiome samples (multiplex ELISA) for analysis and correlation with primary and key secondary endpoints. 10. To describe gene expression patterns (in particular those associated with apoptosis, androgen receptor signaling, c-MET activation, and a c-MET-specific endocytosis panel) correlated with cabozantinib administration using RNA sequencing.

	
 11. To explore changes in serum and intratumoral androgen concentrations related to cabozantinib treatment. 12. To collect cell-free DNA (cfDNA) for analysis and correlation with primary and key secondary endpoints.

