4. To measure expression levels of c-MET, VEGF, and HGF, as well as activation status of c-MET in prostate tissue.	4. Quantification of c-MET, VEGF, HGF, and activated c-MET in prostatectomy tissue	4. To evaluate effects on the c-MET/HGF axis.
5. To describe changes in plasticity signaling markers associated with prostate tumors, including vimentin, AR, SNAIL, AXL, and N-cadherin, with cabozantinib exposure	5. Correlation of changes in vimentin, AR, SNAIL, AXL, and N-cadherin with cabozantinib exposure	5. To describe effects on markers of epithelial-mesenchymal transitions (EMT).
6. To evaluate PTEN and p53 genomic and protein expression status in tumor tissue	6. Measurement of PTEN and p53 genomic and protein expression status in tumor tissue	6. To evaluate whether cabozantinib may be more active in a subset of pTEN/p53-deficient tumors. ¹⁰
7. To demonstrate that cabozantinib is safe and tolerable in patients	7. Adverse events by CTCAE v5.0, dose intensity of cabozantinib.	7. To demonstrate that cabozantinib is safe and tolerable in patients

OBJECTIVES	ENDPOINTS	JUSTIFICATION FOR ENDPOINTS
undergoing radical prostatectomy.		undergoing radical prostatectomy.
8. To demonstrate that surgery is safe and feasible in patients undergoing treatment with cabozantinib.	8. Blood loss at prostatectomy and duration of hospital stay.	8. To demonstrate that surgery is safe and feasible in patients undergoing treatment with cabozantinib.
9. To collect plasma angiome samples (multiplex ELISA) for analysis and correlation with primary and key secondary endpoints.	9. Angiome biomarkers.	9. To collect samples for possible later analysis and correlation with key endpoints
10. To describe gene expression patterns (in particular those associated with apoptosis, androgen receptor signaling, c-MET activation, and a c-MET-specific endocytosis panel) correlated with cabozantinib administration using RNA sequencing analysis.	10. Gene expression patterns.	10. To collect samples for possible later analysis and correlation with key endpoints.
11. To explore changes in serum and intratumoral androgen concentrations related to cabozantinib treatment.	11. Serum and intratumoral androgen concentrations.	11. To collect samples for possible later analysis and correlation with key endpoints.12

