4.2 CORRELATIVE STUDIES

Please see the lab manual for further details of these analyses.

Apoptosis

Cleaved Caspase-3. Caspase-3 is a central downstream executor of both the intrinsic and extrinsic apoptosis pathways, and is responsible for the proteolytic cleavage of key effector molecules such as nuclear poly (ADP-ribose) polymerase (PARP).²⁹ Cleavage of the zymogen form of caspase-3 to its active p17 and p12 fragments by caspase 8,9,10, or 12 is essential for downstream induction of apoptosis. The primary endpoint is comparison of apoptosis in prostatectomy specimens in cabozantinib-treated patients versus controls.

Comprehensive Immune Profiling

We will focus on comprehensive immune profiling of available samples representing the cabozantinib-treated and untreated tumor microenvironment (TE) as well as baseline and longitudinal PBMC samples in cabozantinib-treated and untreated patients in an attempt to identify both: (1) baseline signatures that predict which patients might benefit from cabozantinib, as well as (2) pharmacodynamic signatures that could provide mechanistic insights regarding therapeutic responses. The TE (tissue) will be analyzed in the laboratory of [name] (Duke Chair of Pathology). The profiling platform to be used to analyze the peripheral blood (PBMC) samples will be highly standardized, polychromatic flow cytometry assays that have been developed by the Duke Immune Profiling Core (DIPC; Director: [name]) specifically for monitoring immune signatures in the context of immune checkpoint blockade trials.

Pathologic Response

Complete pathologic response (pCR) is defined as complete resolution of all cancerous glands in the prostatectomy specimen. Patients treated with cabozantinib who have pCR will be defined as *extraordinary responders*. Tissue from these patients' prostate biopsy will be collected for analysis and correlation with key correlative endpoints.

Relapse-free Survival

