total ablation of tissue dihydrotestosterone (DHT) levels and impressive rates of pCR and near-pCR.^{37,38} Given the apparent inverse relationship between the AR and c-MET,³⁹ we hypothesize that patients treated with cabozantinib will have increased intratumoral androgen concentrations relative to the prostatectomy specimens of controls. In prostatectomy specimens, tissue androgen and androgen precursor levels (i.e. testosterone, DHT, DHEA, etc.) will be stored for possible analysis by mass spectrometry (MS) using methods previously described.⁴⁰ The same androgen levels in serum will also be measured at baseline and prior to prostatectomy.

Cell-free DNA (cfDNA)

We will collect double-spun platelet poor plasma EDTA samples for circulating cfDNA analysis. Samples will be stored at -80°C for later analysis in a non-CLIA format.

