5. Day 1 physical exam and KPS do not have to be repeated if screening physical exam and KPS were performed within 7 days prior to Day 1 visit. Vitals signs must be completed on Day 1 regardless of when they were collected during screening.
6. Randomization may take place any time before or on day 1, after the patient is confirmed to be eligible.
7. Cabozantinib will be administered at 40 mg daily for 28 days. A pill diary will be provided to the subject. Study drug will be dispensed directly from the clinic. Unused drug will be returned to the clinic.
8. Prostatectomy will occur 2 weeks (14 + 3 days) after the last dose of cabozantinib. Tissue will be procured for pathologic, molecular, and immunologic assessments.
9. Relapse free survival follow up may be captured over the telephone, clinic visit or chart review every 3 months +/- 1 month.
10. Laboratory assessments at the times indicated include:
 - Complete blood count (CBC) with differential
 - Serum chemistries (CMP): Sodium, Potassium, Chloride, Bicarbonate, blood urea nitrogen (BUN), Creatinine, Glucose, aspartate aminotransferase (AST), alanine aminotransferase (ALT), total bilirubin, alkaline phosphatase, and LDH.
 - Coagulation Factors: PT/INR or PTT will be drawn at baseline only.
 - PSA
 - Testosterone
 - Thyroid function testing: Will include TSH and T4.
 - Urine Protein Creatinine Ratio: $UPCR = (\text{Urine protein mg/dl}) / (\text{urine creatinine mg/dl}) = \text{numerically equivalent to gm protein excreted in urine over 24 hours.}$
 - Notes:** Screening labs (except testosterone) must be completed within 7 days of day 1, or they must be repeated on day 1.
11. CBC with differential, CMP, coagulation factors and urine protein creatinine ratio must be completed within 14 days of Day 1 if subject is assigned or randomized to Arm A: Cabozantinib.
12. Thyroid function tests (TFTs) will be repeated at the safety follow up visit in those who require clinical intervention due to alteration in TFTs at an earlier time point.
13. Immune and androgen correlates will only be collected at baseline and on Day 29.
14. For extraordinary responders (i.e. pCRs) we will obtain archival tissue from their pre-prostatectomy prostate biopsy if available.

FIGURE 3: SCHEDULE OF EVENTS

Arm B: Immediate Prostatectomy

Assessment	Screening	Day	Relapse free Follow up
	D-42 to -1	1 ¹	3 year follow up (from prostatectomy)
Informed Consent	X		
Medical History and Demographics	X		
Interval history ²		X	

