Concomitant Medicines	X		
Physical Exam ³	X		
Karnofsky Performance Status (KPS)	X		
ECG	X		
Randomization ⁴	X		
Prostatectomy ⁵		X	
Phone call or chart review ⁶			X
Laboratory assessments			
CBC with differential ^{7,8}	X		
Serum chemistries (CMP) ^{7,8}	X		
Coagulation factors ^{7,8}	X		
PSA ⁷	X		
Testosterone ⁷	X		
Urine Protein Creatinine Ratio ^{7,8}	X		
Correlative/Research studies			
Plasma/serum cfDNA, immune, androgen and angiome correlates	X		

- 1 For this arm, "Day 1" is defined as the day on which the prostatectomy is performed. While the end of screening is labelled as Day -1 and the prostatectomy as Day 1, these days are not intended to be consecutive. It is expected that there will be intervening days in order to allow scheduling of the prostatectomy.
- 2 Interval history consists of the following:
 - a. Medical history collected as clinically indicated during standard of care clinic visits, which may include disease related symptoms (i.e. pain, changes in urination) and drug related side effects (i.e. bleeding, diarrhea, fatigue, etc.).
 - b. Select imaging to rule out metastatic disease will be done as clinically indicated. Subjects will not routinely receive bone scan, CT, or MRI imaging unless there is clinical concern for possible metastatic disease.

- 3 Vital signs must be performed at screening visit by a medical professional. Blood pressure, temperature, pulse, respiratory rate, height and weight will be collected.
- 4 Randomization may take place any time before or on day 1, after the patient is confirmed to be eligible.
- 5 With tissue procurement for pathologic, molecular, and immunologic assessments.
- 6 Relapse free survival follow up may be captured over the telephone, clinic visit or chart review every 3 months +/- 1 month.
- 7 Laboratory assessments at the times indicated include:
 - Complete blood count (CBC) with differential
 - Serum chemistries (CMP): Sodium, Potassium, Chloride, Bicarbonate, blood urea nitrogen (BUN), Creatinine, Glucose, aspartate aminotransferase (AST), alanine aminotransferase (ALT), total bilirubin, alkaline phosphatase, and LDH.
 - Coagulation Factors: PT/INR or PTT.
 - PSA
 - Testosterone
 - Urine Protein Creatinine Ratio: $UPCR = (\text{Urine protein mg/dl}) / (\text{urine creatinine mg/dl}) = \text{numerically equivalent to gm protein excreted in urine over 24 hours.}$

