Sample Size Justification. The primary endpoint of this randomized phase II study is the apoptotic index by cleaved caspase-3 in prostatectomy specimens following 4 weeks of treatment with cabozantinib compared with prostatectomy specimens of untreated patients. The target sample size of convenience is 30 patients where the randomization allocation ratio will be 2:1 cabozantinib-to-control. The randomization will not be stratified on any variable. The null hypothesis is that the mean apoptotic indices are equal between the two groups. The percent of tumor cells positive for cleaved caspase 3 staining for each patient will be evaluated for the primary objective. The 6 subjects assigned during the Safety Lead-In Cohort are included in the 30 patient sample size and 2:1 randomization allocation ratio.

Based on data from a prior, unpublished pre-prostatectomy study of sunitinib, we expect the controls to have minimal staining (i.e., $\leq 5\%$). In the proposed study we will enroll 10 controls and 20 cabozantinib-treated patients to demonstrate increased staining (i.e., $>5\%$). A two sample t-test will be used to compare group means. With 10 and 20 evaluable patients in the control and cabozantinib-treated groups, respectively, the test will provide 70% power to detect a mean (for positive tumor cells percentage) difference of one-fold standard deviation based on a two-sided type I error of 0.05; or 96% power to detect an one-and-half fold standard deviation difference. Assuming a 10% unevaluable rate, we will enroll up to 33 patients total to have 30 evaluable patients.

Data Analysis. Box plots and statistical summaries of apoptotic (cleaved caspase-3, TUNEL), proliferation (Ki-67), and MVD (CD31) indices will be presented. In addition, the t-test will be used to compare the two arms on apoptotic index, proliferation and MVD indices. Further, the Chi-square test will be used to compare the two treatment arms on pathologic complete response rate (pCR) and pathologic T2 (pT2) rate. The angiome, gene expression, cell-free DNA and mesenchymal markers analyses will be reported descriptively as the trial's limited sample size will not permit definitive analyses for these exploratory objectives. The t-test will be used to compare the two arms' serum and tissue androgen and androgen precursor levels.

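### The two-arm serum androgen t-test names no time point, and with a single Arm B draw at screening it cannot be a controlled drug comparison; the within-patient change that Arm A does sample has no planned analysis

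*Combined protocol and SAP*

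**What the plan says.** - **Objective.** Exploratory objective 11 (Synopsis; Section 3) is "To explore changes in serum and intratumoral androgen concentrations related to cabozantinib treatment". Section 3 justifies it as "To collect samples for possible later analysis and correlation with key endpoints".
- **Analysis.** The Data Analysis paragraph of Section 11.1 plans a t-test between the two arms on "serum and tissue androgen and androgen precursor levels". It gives no time point, change score or baseline adjustment.
- **Sampling as described.** Section 4.2, under Intratumoral Androgens, says "The same androgen levels in serum will also be measured at baseline and prior to prostatectomy", without limiting this to one arm. Under Comprehensive Immune Profiling it refers to "baseline and longitudinal PBMC samples in cabozantinib-treated and untreated patients".
- **Sampling as scheduled.** Section 6 says correlative blood will generally be "drawn at baseline, day 29, and day 57-85 in the cabozantinib arm and baseline in the immediate prostatectomy arm", and refers to Figures 2 and 3 for full details. Figure 2, note 13, narrows Arm A: "Immune and androgen correlates will only be collected at baseline and on Day 29". In Figure 3 the Arm B row "Plasma/serum cfDNA, immune, androgen and angiome correlates" is marked at screening only. The surgery-day lists (Section 6.11 for Arm A, Section 6.14 for Arm B) contain the operation and tissue, and no blood.

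**The concern.** A two-arm serum comparison informs on the drug only if the arms are sampled at comparable times, with at least one sample taken after treatment has begun in Arm A. Arm B has no blood after screening. Because Section 11.1 does not say which Arm A draw enters the test, the choice stays open until the data are seen. One choice answers no drug question, and the other can be mistaken for a controlled comparison. Meanwhile the paired Arm A draws, the only serum data that measure the change objective 11 asks about, have no planned analysis.

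**Working it through.** **1. The plan's own figure.** Section 11.1 states 70% power at 1 SD and 96% at 1.5 SD for the primary endpoint with 10 and 20 patients, two-sided 0.05. The standard error of the difference is sqrt(1/10 + 1/20) = 0.387 SD. The noncentral t with 28 df gives 70.3% and 96.2%, so the stated power reproduces. No power is stated for androgens. The same 0.387 SD applies to a two-arm serum test on 20 and 10 patients.

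**2. Blood draws by arm (Figures 2 and 3; Sections 6.11 and 6.14).**

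| | Arm A | Arm B |
|---|---|---|
| Androgen correlates | Screening, Day 29 | Screening |
| Routine testosterone | Screening, Day 29, Day 57-85 (post-surgery) | Screening |
| Blood listed on surgery day | None | None |
| Change scores available | Up to 20 | 0 |

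Routine testosterone does not fill the gap: it too is screening-only in Arm B.

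**3. What the test can be.**
- (i) Baseline against baseline: both values precede treatment, so there is no drug effect to find.
- (ii) Arm A Day 29 against Arm B screening: it can be computed, but it sets on-drug values in some patients against untreated values in others. Day 29 falls a nominal 29 days (from Day -1) to 70 days (from Day -42) after screening, with no Day 0 and visit windows ignored.

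**4. Precision of (ii) against the Arm A paired change.** Assume equal SDs at the two draws and a within-patient correlation rho. The documents give neither, so a range is shown. Paired SE = sqrt(2(1 - rho)/20). Power and detectable change use the noncentral t, two-sided 0.05, with 19 df (paired) or 28 df (two-group).

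| | rho 0 | rho 0.3 | rho 0.5 | rho 0.7 | Version (ii) |
|---|---|---|---|---|---|
| SE, 20 pairs (SD) | 0.316 | 0.265 | 0.224 | 0.173 | 0.387 |
| SE, 16 pairs (SD) | 0.354 | 0.296 | 0.250 | 0.194 | – |
| Power at 0.75 SD | 61% | 77% | 89% | 98% | 46% |
| Change detectable at 80% power (SD) | 0.93 | 0.78 | 0.66 | 0.51 | 1.12 |

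Break-even: 2(1 - rho)/20 = 0.15 gives rho = -0.5. If the Day 29 SD is k times the screening SD, the paired SE is smaller when (1 + k² - 2·rho·k)/20 < k²/20 + 1/10, that is, when rho·k > -0.5. The paired form therefore wins at any non-negative correlation, whatever k is.

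**5. Neither form separates drug from time.** Suppose there is no drug effect but serum values drift between screening and Day 29. For an assumed drift of 0, 0.25, 0.5 or 1 SD, version (ii) rejects in 5.0%, 9.6%, 23.9% or 70.3% of trials. The paired test, being more precise, picks up drift more readily: at 0.5 SD it rejects in 43%, 57% or 78% of trials at rho 0.3, 0.5 or 0.7. Its result must be reported as change over the treatment period, not as a drug effect.

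**6. Using the Arm B screening values.** A longitudinal model with a common baseline mean over all 30 patients has SE = sqrt((1 - rho²)/20 + (1 - rho)²/30) = 0.289, 0.249, 0.214 or 0.169 SD at rho 0, 0.3, 0.5 or 0.7. That is about 3% to 9% below the paired SE. It assumes equal baseline means in the two arms, which randomisation supports for 14 of the 20 Arm A patients; the other 6 are the assigned lead-in.

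**The case against.** The strongest reply is that Section 11.1 tests levels, not change, and that setting Arm A Day 29 against Arm B's only untreated value is a legitimate test of levels. That is right as far as it goes: a reader might infer that the test cannot be computed, or that a planned change analysis has failed, and the documents support neither. What stands is that the plan does not say which comparison is meant, and that neither available one is controlled.

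Section 4.2 can also be read less strictly. Its sentence on serum androgens does not say that both arms are drawn twice. Its PBMC wording concerns available samples and a descriptive aim. A reader might infer a promised between-arm test of blood change, or damage to the secondary immune endpoint. But Section 11.1 plans no test on PBMC, and the endpoint is worded as a description. Only the reference to longitudinal samples in untreated patients conflicts with Figure 3.

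The time mismatch is no reason to prefer the paired form. The documents give no evidence of drift in untreated men, and drift would affect both forms. The case for pairing is precision and fit to objective 11.

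The lab manual, which is not among the documents, might list further draws. Section 6, however, refers to Figures 2 and 3 for full details, and an extra Arm B draw would contradict Figure 3.

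Finally, a second, pre-surgery Arm B draw would allow a two-arm test of change, with 56%, 70%, 90% or 98% power for 1 SD at assumed rho 0.3, 0.5, 0.7 or 0.8. That is a real alternative, but it needs a new sample.

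**Conclusion.** The point holds and is minor. As scheduled, the serum androgen t-test is either uninformative about cabozantinib or an uncontrolled contrast between different patients, with a standard error of 0.39 SD. The paired Arm A change has 0.32 to 0.17 SD over assumed correlations of 0 to 0.7, uses samples already planned, and addresses objective 11. The direction needs only a non-negative within-patient correlation; the exact sizes rest on the assumed correlations, equal SDs and 20 complete pairs.

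The consequence is confined to one exploratory analysis. The primary cleaved caspase-3 comparison and its stated power do not depend on blood. The tissue androgen t-test fits the schedules, because tissue is taken at prostatectomy in both arms.

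**What to change.** - In Section 11.1, replace the two-arm serum androgen t-test with a paired analysis of Day 29 minus screening in Arm A. Arm B screening values may be pooled into the baseline in a longitudinal model.
- State that this change is uncontrolled and does not separate drug from time, and that no between-arm on-treatment serum claim will be made.
- Keep the tissue androgen t-test as it is.
- In Section 4.2, align the serum androgen sentence, and the wording on longitudinal PBMC in untreated patients, with Figures 2 and 3.

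The cost is wording in Sections 4.2 and 11.1, with no new sample, visit or patient. What is given up is a nominal two-arm serum comparison that could not have shown a controlled drug effect. If the sponsor wants a controlled serum comparison, it would have to add a pre-surgery draw in about 10 Arm B patients and list it in Figure 3.
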